6.6.2. During hospitalisation

During hospitalisation, patients will have blood taken for malaria films and haematocrit at 4h, 8h and 12h and thereafter every 6 hours until parasite clearance (when two consecutive malaria slides are negative). Haematocrits will be done whenever a malaria blood film is made.

During hospitalisation (24 hr, 48 hr 72 hr and 96 hr and follow-up visits (day 7, 14, 21, 28), blood will also be taken for:

- 1 mL EDTA: Full blood count, , and Hb
- Reticulocyte count
- 1 mL heparinised blood: biochemistry assessments including bilirubin, ALT, AST, Alkaline Phosphatase, and creatinine levels, and LDH.

Other tests that might be deemed relevant by the treating physician for the care of the patients can be performed.

Note: Once parasitemia has been cleared and the patient tolerates oral antimalarial medications. The patients can be discharged according to the judgement of treating physician.

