7.2 Compliance with Study Drugs

Parenteral study drugs will be administered by study medical staff (either a doctor or nurse). The first dose of ACT will be administered by DOTs and if the patient vomits ACT, and is re-dosed; this will be recorded in the CRF. If vomiting within 1 hour occurs again after retreatment, no repeat dosing is allowed. In this case the patient will be treated at the discretion of the Investigator. The patient may be discharged if recovered in the opinion of the study physician even if the full 3-day course of ACT is not complete. All drug doses will be recorded in the CRF.

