2.2.1 Determination of sample size

Sample size calculations for non-inferiority study is based on dissolution test data from Guilin Pharmaceutical Co. Ltd. ("Study report on the solubility of artesunate for injection (60mg), Doc. RR-QC-ZSYQHHZ (60mg)RJX-2021 30th April 2021).²³ This is supported by unpublished in-house experience (from a bioequivalence study in healthy volunteers, personal communication, [name], Mahidol University) that the conventional formulation takes about 4 minutes with a standard deviation of 2 minutes to administer injectable artesunate. Our non-inferiority margin is 1 minute of drug re-constitution for the new simpler artesunate formulation i.e. if participants in the 1-step artesunate formulation will have a mean of the time of 5 minutes or less of drug re-constitution, with a standard deviation of 2 minutes, then the new formulation will be considered to be non-inferior to the old formulation. With this non-inferiority margin, detecting non-inferiority with 90% power and with a one-sided alpha of 0.025, we will need to recruit 85 participants in the new formulation and 85 in the old formulation arm giving a total of 170 participants. In order to compensate for a 15% loss to follow-up or withdrawal, we will need 100 participants in each arm giving a total of 200 participants in the two arms combined. These calculations were performed in Stata 16 (StataCorp LLC Software).

The sample size calculation dovetails with pragmatic needs for the other study activities the 200 participants provides sufficient variability of participant characteristics to allow staff to gain experience of using 1-step artesunate and be able to provide an informed opinion of its pros and cons. Recruitment of 100 patients per site is feasible over 12 months based on the expected numbers of cases of severe malaria ([name] and [name], personal communication April 2021). The sample size calculation is based only on the time-to-treatment of participants and not on the costing analysis.

STATISTICAL ANALYSIS PLAN

3. Data Analysis

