3.4 Fever clearance and parasite clearance during treatment, by treatment allocation

Table 4 Clinical recovery*, fever clearance, and parasite clearance by study arm**

	1-STEP AS N=XXX	2-STEP AS N=XXX	Both groups N=XXX	P- value (2-sided)
Hours to fever clearance, mean (SD) (baseline to start of first 24h period <37.5C; temperature was recorded every 4 hours, until day 2, then 6 hourly)				
DRC	XX.X (X.X)	XX.X (X.X)	XX.X (X.X)	X.XXX
Tanzania	XX.X (X.X)	XX.X (X.X)	XX.X (X.X)	X.XXX
All study sites	XX.X (X.X)	XX.X (X.X)	XX.X (X.X)	X.XXX
Day 3 blood smear still positive, n/N (%)** (taking prior clearance or discharge as negative)				
DRC	XX/XXX (XX)	XX/XXX (XX)	XX/XXX (XX)	X.XXX
Tanzania	XX/XXX (XX)	XX/XXX (XX)	XX/XXX (XX)	X.XXX
All study sites	XX/XXX (XX)	XX/XXX (XX)	XX/XXX (XX)	X.XXX
Hours to tolerate oral medication, mean (SD)* (baseline to start of oral ACT)				
DRC	XX/XXX (XX)	XX/XXX (XX)	XX/XXX (XX)	X.XXX
Tanzania	XX/XXX (XX)	XX/XXX (XX)	XX/XXX (XX)	X.XXX
All study sites	XX/XXX (XX)	XX/XXX (XX)	XX/XXX (XX)	X.XXX
Parasite clearance half-life in hours, mean (SD)** (excluding patients with initial count insufficient to estimate half-life)				
DRC	X.X (X.X)	X.X (X.X)	X.X (X.X)	X.XXX
Tanzania	X.X (X.X)	X.X (X.X)	X.X (X.X)	X.XXX
All study sites	X.X (X.X)	X.X (X.X)	X.X (X.X)	X.XXX

*Protocol recommends patients receive a minimum of 3 doses of injectable artesunate before switch to oral ACT. Patients may vary if discharged before 24 hours, died, or referred.

** Parasite dynamics will be affected by patients who are transfused.

STATISTICAL ANALYSIS PLAN
3.5 Safety assessments and tolerability (Incidence of adverse events and serious adverse events by study arms within the first 28 days)

Safety analyses will be based on the whole population that get administered the study drug. That is, the safety and tolerability data will be pooled from all the sites that received the same antimalarial treatment.

The safety and tolerability of 1-STEP AS versus 2-STEP AS will be assessed by comparing the frequency (%) of adverse events and serious adverse events, with particular attention to the variables listed below, which pertain to severe malaria.

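### The day-3 smear row in SAP Table 4 scores children discharged without documented clearance as negative, so reported positivity can only err downward

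*SAP*

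**What the plan says.** SAP section 3.4, Table 4, has a row headed "Day 3 blood smear still positive", given as n/N (%) by arm, for each site and overall, with a two-sided p-value. Its scoring note reads "taking prior clearance or discharge as negative". No condition is placed on the last slide before discharge, and deaths, referrals and withdrawals before day 3 are not mentioned.

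Protocol 6.6.2 has films taken at 4, 8 and 12 hours and then every 6 hours, "until parasite clearance (when two consecutive malaria slides are negative". (Protocol 6.6.3 and Appendix 3 change to 12-hourly after hour 48.)

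The protocol speaks of discharge in two places:

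- The closing note of Protocol 6.6.2: "Once parasitemia has been cleared and the patient tolerates oral antimalarial medications. The patients can be discharged according to the judgement of treating physician".
- Protocol 7.2, on compliance: "The patient may be discharged if recovered in the opinion of the study physician". The sentence goes on to say that this applies even when the 3-day ACT course is unfinished. It does not mention smears.

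A footnote to Table 4, marked with a single asterisk, adds "Patients may vary if discharged before 24 hours, died, or referred".

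**The concern.** The scoring note joins two different states. Clearance is a laboratory finding. Discharge is an administrative event that says nothing about parasites unless a slide requirement goes with it. Once clearance has its own definition, the discharge half of the note can act only on children who do not meet that definition. A child whose last film was positive, and who then went home, would be entered as negative.

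Protocol 3.2 says parasite clearance is recorded as a precaution against an unexpected difference in drug activity. A row that can err in only one direction, towards fewer positives, is a weak contribution to that check. Protocol 6.3 has laboratory work done without knowledge of allocation, but the trial is open-label. For these children the note therefore replaces a masked slide reading with a decision by staff who may know the arm. The row also carries a p-value, so it will be read as a comparison between arms.

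**Working it through.** **Step 1. Which children the discharge clause affects.** Take every child without a day-3 smear and ask what the note does.

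| Status before day 3 | Covered by prior clearance? | Score under the note |
|---|---|---|
| Two consecutive negative slides, then home or films stopped | Yes | Negative, supported by slides |
| Discharged, last slide positive | No | Negative, by discharge alone |
| Discharged after a single negative slide | No | Negative, by discharge alone |
| Died or referred | No | Not stated |

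The words *or discharge* change the score only in the second and third rows. In the first row they are redundant.

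**Step 2. Whether such children can exist.** Under the note in Protocol 6.6.2, discharge follows clearance and oral tolerance, so those two rows would be empty. Under Protocol 7.2, discharge rests on the physician's opinion of recovery and no slide is required. Protocol 6.8 also lets a caregiver end participation at any time. The documents therefore allow such children but do not say how many there will be.

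**Step 3. The denominator.** The plan gives no expected figure for this row, so the only planned number to carry over is 100 per arm from SAP 2.2.1. That number reproduces. The inputs are "Our non-inferiority margin is 1 minute of drug re-constitution", "the conventional formulation takes about 4 minutes with a standard deviation of 2 minutes", 90% power and one-sided alpha 0.025:

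n = 2 × (1.960 + 1.282)² × 2² / 1² ≈ 84.1, rounded up to 85 per arm (86 with the t distribution); 85 / (1 − 0.15) = 100.

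This calculation concerns preparation time. It supplies N = 100 for the illustration and nothing more.

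**Step 4. Size in one arm.** Let x be the positive day-3 smears, D the children discharged before day 3, and q the share of D without clearance.

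- Reported under the note: x / N
- Upper bound, all uncleared discharges counted positive: (x + D × q) / N
- Largest possible understatement: D × q / N

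The values of x, D and q are assumptions. With x = 5 and N = 100 the note gives 5.0% throughout:

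| D | q = 0 | q = 10% | q = 50% |
|---|---|---|---|
| 10 | 5.0% | 6.0% | 10.0% |
| 20 | 5.0% | 7.0% | 15.0% |
| 40 | 5.0% | 9.0% | 25.0% |

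For D = 10 and q = 50%, five children leave uncleared: 5/100 = 5% reported, (5 + 5)/100 = 10% at most. Leaving those five out of the denominator gives 5/95 = 5.3%. The note always returns the lowest value that these discharges allow.

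**Step 5. Between arms.** Assume true day-3 positivity of 10% in both arms, unrelated to discharge, and early discharge of 30% in one arm and 10% in the other. Reported: 10% × (1 − 0.30) = 7.0% and 10% × (1 − 0.10) = 9.0%. A 2-point difference appears where none exists. With equal early discharge the reported difference is zero.

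**The case against.** The best defence is that discharge already implies clearance. The note in Protocol 6.6.2 links the two. Protocol 7.2 sits under compliance and is about leaving before the ACT course is complete, so its silence on slides need not override that note. Early departure is also not the default. Protocol section 6 encourages families to stay until the ACT course is finished. With injections at 0, 12 and 24 hours and ACT starting 8 hours after the last dose (Appendix 3), that course begins at about 24 + 8 = 32 hours at the earliest. A child who stays for it is still an inpatient at 72 hours. The footnote on very early exits is tied by its single asterisk to clinical recovery and time to oral medication. The day-3 row carries only the double-asterisk note on transfusion.

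All of this stands and limits how many children are affected. It does not support the clause: where discharge does imply clearance, the clause does nothing and can be deleted without loss.

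A reader might go further in three ways, and the documents support none of them.

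- **That every discharged child is miscounted.** Only those who leave before the day-3 smear without documented clearance are affected.
- **That the rule conceals a loss of drug activity.** Day-3 positivity is in neither endpoint list (Protocol 5.4.3, SAP 2.1.3), and Protocol 3.2 says the study is not powered for efficacy comparisons. Parasite clearance half-life is a separate row of the same table, to which the discharge clause does not apply.
- **That the comparison is biased between arms.** That requires uncleared discharge to differ by arm. Open-label care makes this possible, but nothing in the documents shows it.

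**Conclusion.** The point holds as a defect in a stated scoring rule. The clause can enter a child with a positive last slide as negative, and any error it makes lowers reported positivity. The understatement in an arm is at most the number discharged uncleared divided by N. It is zero if every discharge follows clearance, and 1 to 20 percentage points across the assumed range of 10 to 40 early discharges per 100 with 10% to 50% of them uncleared. The top of that range treats every uncleared child as still positive on day 3, which is an upper bound because children under treatment may clear after leaving.

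The documents give neither discharge rates nor expected day-3 positivity, so the actual size is unknown. A distorted comparison between arms is possible but not demonstrated. The row is exploratory and unlisted, and neither co-primary endpoint (time to administration, cost) is affected. The correction is still worth making before the data are analysed.

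**What to change.** Change the note to the day-3 row of SAP Table 4 as follows.

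1. Delete the discharge clause. Score a child without a day-3 smear as negative only if two consecutive negative slides were recorded earlier.
2. Report all other children without a day-3 smear (discharged uncleared, died, referred, withdrawn) as not assessed, with counts and reasons by arm, and leave them out of the main n/N.
3. Add sensitivity bounds that count the not-assessed children first all as positive and then all as negative. Classification by last slide can be a further sensitivity analysis. It should not be the main one, because a child positive at about 30 hours may be clear by 72 hours.

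The discharge wording in Protocol 6.6.2 and 7.2 must also be reconciled so that the analysis rests on one stated practice. No view is taken here on which is right.

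The cost is one table note and a few extra table lines, using slides that are already read. The small downside is a slightly smaller denominator, for example 95 instead of 100 if five children are not assessed.

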APPENDIX 1. DOSING SCHEDULES

The dosing scheme for parenteral artesunate is 2.4 mg/kg at hour 0, hour 12, hour 24, and each 24 hours until the patient can take oral medication. Children <20 kg will get 3.0 mg/kg. At least 3 parenteral doses should be given before switching to oral therapy can be considered i.e.: stop injectable artesunate and give oral antimalarial. When the patient is improving and able to take oral tablets a switch to oral ACT should be considered.

2-step conventional injectable artesunate. Refer to Artesun SmPC page 2&3.

One unit box of Artesun (conventional injectable artesunate) contains:

Each vial contains: artesunate powder 60 mg

Each ampoule of solvent contains: sodium bicarbonate 50 mg/ml, 1 ml

Each ampoule of diluent contains: sodium chloride 9 mg/ml, 5ml (There is no need to use additional 5% dextrose for dilution.)

For intravenous (IV) injection (10 mg/ml)

After reconstitution and dilution one ml of solution for injection contains 10 mg artesunate.

Using a syringe, add 5 ml of sodium chloride 0.9% for injection to the vial containing the reconstituted artesunate solution. This will yield 6 ml of a solution containing artesunate 10 mg/ml. Shake to mix well, ensuring that the resulting solution is still clear. If the solution appears cloudy or a precipitate is present, it should be discarded.

The volume of the solution required (ml) will be:

Volume (ml) = [dose (mg)] ÷ 10

For intramuscular (IM) injection (20 mg/ml)

After reconstitution and dilution one ml of solution for injection contains 20 mg artesunate.

Using a syringe, add 2 ml of sodium chloride 0.9% for injection to the vial containing the reconstituted artesunate solution. This will yield 3 ml of a solution containing artesunate 20 mg/ml. Shake to mix well, ensuring that the resulting solution is still clear. If the solution appears cloudy or a precipitate is present, it should be discarded.

The volume of the solution required (ml) will be:

Volume (ml) = [dose (mg)] ÷ 20

1-step injectable artesunate. Refer to Argesun SmPC page 2&3.

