APPENDIX 3. TIME AND EVENT SCHEDULE

TEST/APPLICATION	SAMPLE	SCR	Day 0					Day 1				Day 2				Day 3				Discharge day	Day 7	Day 14	Day 21	Day 28	F/U for sequeale*****								
			H0	H4	H8	H12	H18	H24	H30	H36	H42	H48	H54	H60	H66	H72	H78	H84	H90		**** ***	**** ***	**** ***	**** ***	Month 3	Month 6	Month 12						
Informed Consent		X																															
Demographic/ drug history		X																															
Medical history		X																													X	X	X
Temperature*		X	X	X	X	X	X	X	X	X	X	X	X	X	X	X	X	X	X			X	X	X	X	X	X	X	X	X	X	X	X
Vital signs**		X	X	X	X	X	X	X	X	X	X	X	X	X	X	X	X	X	X			X	X	X	X	X	X	X	X	X	X	X	
Weight/Height		X																															
Physical examination		X					X				X				X						X	X	X	X	X	X	X	X	X	X	X	X	
Neurological exam																				X					X	X	X	X	X	X	X	X	
Symptom questionnaire			X				X				X				X						X	X	X	X	X	X	X	X	X	X	X	X	
Randomisation			X																														
Injectable artesunate***			X			X	X																										
Oral ACT****									(X)		(X)				(X)				(X)														
SAMPLE COLECTION																																	
Malaria RDT		X																															
Malaria blood film*****	EDTA	X	X	X	X	X	X	X	X	X	X	X	X	X	X	X	X	X	X	X	X	X	X	X	X	X	X	X	X	X	X	X	
Haematocrit*****	EDTA	X	X	X	X	X	X	X	X	X	X	X	X	X	X	X	X	X	X	X	X	X	X	X	X	X	X	X	X	X	X	X	
Haemoglobin	EDTA		X				X				X				X						X					X	X	X	X				
Blood glucose*****			X	(X)	(X)	(X)	(X)	(X)																									
Full Blood Count	EDTA		X				X				X				X						X					X	X	X	X				
Biochemistry*****	EDTA		X				X				X				X						X					X	X	X	X				
Reticulocytes	EDTA		X				X				X				X						X					X	X	X	X				

*Temperature measured at time of malaria blood film until 2 consecutive measurements below 37.5°C

**Vital signs recorded hourly for unstable patients, then 6 hourly for stabilised patients, and at each F/U visit.

***Injectable artesunate at 0, 12, 24 hrs and until able to tolerate oral medication

**** Oral ACT starts 8 hours after the last dose of iv artesunate. ACT for 3 days, first dose directly observed and then DOTs on study wards if patient agrees, or patient can be discharged to complete treatment at home.

*****Malaria blood film and HCT taken at admission and 0h, 4h, 8h and 12h, then +6 hourly until H48, then 12 hourly until 2 consecutive negative slides, day 7, 14, 21, 28, and unscheduled (n).

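### Fever clearance and time to oral ACT are compared as mean hours, with no rule for children who die, are referred or leave before the event

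*SAP*

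**What the plan says.** Two rows of SAP Table 4 (section 3.4) are durations to an event, each shown by arm and by site with a two-sided p-value:

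- "Hours to fever clearance, mean (SD) (baseline to start of first 24h period <37.5C"
- "Hours to tolerate oral medication, mean (SD)* (baseline to start of oral ACT"

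A footnote attached to the table title and to the oral-medication row, but not to the fever row, reads "Protocol recommends patients receive a minimum of 3 doses of injectable artesunate before switch to oral ACT" and continues "Patients may vary if discharged before 24 hours, died, or referred". Nothing says how such children enter the analysis. Two other rows of the table do carry a rule: the day 3 smear row counts cleared or discharged children as negative, and the half-life row excludes children whose starting count is too low.

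The general approach in the SAP is a t-test, with a Mann-Whitney test as an option for strongly skewed data. Its general intention-to-treat statement is limited to the primary outcome. No censoring, competing-event or time-to-event method is named for these rows.

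On when oral treatment can begin, Protocol Appendix 1 says "At least 3 parenteral doses should be given before switching to oral therapy can be considered" and Protocol Appendix 3 says "Oral ACT starts 8 hours after the last dose of iv artesunate". Protocol section 5.4.3 defines the endpoint as time from the start of parenteral treatment to oral ACT, and lists both outcomes as exploratory. SAP section 2.1.3 lists them as secondary.

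**The concern.** Both outcomes are times to something that some children will not reach under observation. A mean needs an observed number for every child who contributes, so without a rule it becomes an average over those who reached the event. That group is formed after randomisation, and the comparison of its means is no longer protected by randomisation.

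The loss is foreseeable. Protocol Appendix 4 describes high mortality in severe malaria, with deaths concentrated in the first day after admission. The trial is open-label, so decisions on referral, discharge and the switch to oral treatment are made knowing the arm, and unequal loss is plausible.

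Protocol section 3.2 presents the parasite clearance data as a precaution against an unexpected, substantial difference in drug activity. The recovery times in the same table serve a similar reassurance, and a summary restricted to children who recover under observation serves it poorly.

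A second, smaller matter concerns the oral row. Its label speaks of tolerating oral medication, but what is measured is the start of ACT, which depends partly on the dosing timetable.

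**Working it through.** **1. The plan's own figure.** There is none for these endpoints. The only sample-size calculation concerns preparation time (margin 1 minute, SD 2 minutes, one-sided 0.025, 90% power). It reproduces: 2 × (1.960 + 1.282)² × 2² / 1² = 84.1, rounded up to 85 per arm, and 85 / 0.85 = 100 per arm. It has no bearing on Table 4.

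**2. Who can have an event time.**
- *Fever clearance* needs a completed 24 h period below 37.5°C. A child who dies or leaves observation within 24 h of baseline cannot complete one.
- *Oral ACT* under Appendix 3 follows the 24 h dose by 8 h. A child who dies in the first day never starts it.
- *Discharge* is different. Protocol section 6.6.2 allows it once parasites are cleared and oral medication is tolerated, and section 6.7 has the first ACT dose directly observed. A child sent home well before 24 fever-free hours are documented is probably a fast recoverer.

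**3. What a mean of observed times does.** With a share f of an arm missing:

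mean of observed = mean of all − f × (mean of missing − mean of observed)

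The between-arm error is the difference of this last term between arms. It cancels when loss is alike in both arms. For a child who dies, the missing time does not exist, which is why a competing-event analysis is needed and imputation is not enough.

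**4. Illustration for the oral-ACT row. Every input is assumed.** Time to readiness for oral treatment is lognormal, median 30 h, log-SD 0.5, the same in both arms. ACT starts at the later of readiness and 8 h after the last scheduled dose (24 h at the earliest, then daily). The chance of being lost rises with slowness (logit slope 1.5 per SD of log time). One million children were simulated per arm. The mean over all children is about 39.9 h in every arm.

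| Loss, arm A / arm B | Observed mean A (h) | Observed mean B (h) | B − A (h) |
|---|---|---|---|
| 5% / 5% | 38.73 | 38.71 | −0.02 |
| 10% / 10% | 37.87 | 37.87 | 0.01 |
| 5% / 10% | 38.71 | 37.88 | −0.84 |
| 5% / 15% | 38.72 | 37.12 | −1.60 |

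With 100 children per arm, the last two rows mean 5 against 10 and 5 against 15 children without a time. Equal loss lowers both means (by about 1.2 h at 5% and 2.1 h at 10%) but creates no arm difference. If the lost children are the fast ones, the sign reverses.

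**5. The minimum for oral ACT.** Doses at 0, 12 and 24 h, then 8 h: 24 + 8 = 32 h. After further daily doses: 48 + 8 = 56 h and 72 + 8 = 80 h. Under the same assumed switching rule, with no loss, the share of comparator children at exactly 32 h is Φ(ln(32 / median) / 0.5). If recovery is truly 20% faster in one arm, the true mean difference is 0.2 × median × exp(0.125). The last column is simulated.

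| Assumed median (h) | At 32 h | True difference (h) | Difference seen (h) |
|---|---|---|---|
| 16 | 92% | 3.6 | 0.5 |
| 24 | 72% | 5.4 | 2.2 |
| 36 | 41% | 8.2 | 5.9 |
| 48 | 21% | 10.9 | 9.6 |

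The minimum shrinks a real difference. It does not create one, because it is the same in both arms.

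**The case against.** The other side has several good points.

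- **The SAP does not say these children are excluded.** A reader might infer a stated exclusion, but the document is silent. The gap is a missing rule, although a mean with no rule leads to the same place.
- **The 32 h minimum is narrower than it looks.** A reader might apply it to both rows or treat it as fixed. Fever clearance has no such minimum. For oral ACT, the 8 h lag appears only in Appendix 3. Appendix 1 asks for three doses and, for the new product, at least 24 hours. Protocol section 6 leaves the timing of oral treatment to the clinician, and the SAP footnote speaks of a recommendation. How far the row reflects the timetable depends on an unknown recovery time: 21% to 92% of children sit at 32 h across the assumed medians.
- **The direction is not known.** It is tempting to say that an arm with more deaths will look faster. Deaths and referrals are probably slow recoverers, but early discharges may be fast ones.
- **Large figures are easy to produce.** Taking 10% missing with an assumed extra 48 h gives 0.10 × 48 = 4.8 h. That is a shift in one arm's mean and becomes a between-arm error only if the other arm loses nobody.
- **Other outputs give partial cover.** The CONSORT diagram shows losses by arm, Table 5 shows serious adverse events, and a Mann-Whitney test is allowed.
- **The stakes are limited.** Protocol section 3.2 says the study is not powered for these outcomes.

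These points limit the size and certainty of the claim. They do not supply the rule. A rank test still needs a value for each child, and counts of losses or serious events elsewhere do not correct a mean in Table 4.

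**Conclusion.** The point holds in a limited form. Table 4 tests mean hours for two outcomes that some children cannot have, and neither document says what happens to those children. Unless values are imputed, the result describes only children who reach the event, and it is biased if the losses differ by arm.

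The size cannot be read from the documents, which give no expected rate of death, referral or early discharge. On the assumptions shown for the oral-ACT row, the spurious difference is nil with equal loss, about 0.8 h at 5% against 10%, and about 1.6 h at 5% against 15%. No figure was derived for fever clearance.

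The 32 h minimum is a separate and lesser matter. It concerns the oral-ACT row only, holds for children who follow Appendix 3, and dilutes the comparison without biasing it. It does make the row a poor measure of when a child could tolerate oral medication.

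The change is worth making because it is standard and cheap. The co-primary results do not depend on it.

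**What to change.** In SAP section 3.4 and Table 4:

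1. Analyse both outcomes from first dose in all randomised children, as cumulative incidence curves by arm, with death and referral before the event as competing events. State how a child randomised but never dosed is counted.
2. Compare arms with a site-stratified test: Gray's test, or a cause-specific hazard ratio named as such, with 95% CI. If the hazard ratio is used for oral ACT, state the handling of ties, since start times may cluster.
3. State the rule for discharge before the event. Because discharge depends on recovery, add a sensitivity analysis, for example censoring at discharge against counting a child discharged well as having reached the event.
4. Report by arm the number without an event and the reason.
5. Keep mean (SD) as description, labelled as covering children with an observed event.
6. Rename the oral-medication row *time to start of oral ACT*, in line with Protocol section 5.4.3, and report the number of parenteral doses before the switch by arm.

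The statements on the timing of the switch in Protocol section 6 and Appendices 1 and 3 must be reconciled. Which one is right is not a statistical question.

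The cost is a revised table and modest extra programming. Drug doses are already recorded in the CRF and temperatures are scheduled; SAP section 1.4 allows R as well as Stata. No change to patient care is involved.
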